#### *Diagnosis >age 50 cohort*

We expect 26% of participants diagnosed after age 50 will have Type 1 diabetes using the study definition, based on analysis of study primary outcome in population based cohort (DARE study – prevalence T1D as defined by primary outcome where insulin treated within 12 months of diagnosis 48%, prevalence where non-insulin treated at diagnosis 3.9%). Assuming the primary outcome is available in 90% of participants (higher retention expected in older participants) this will give confidence intervals of 85-94% and 87-92% around a biomarker sensitivity/specificity of 90% for Type 1 diabetes.

### 9.2 Feasibility

With >200 new cases of diabetes per 100,000 population annually in the <=age 50 age group this sample size represents <6% of expected incidence at each centre for the recruitment period. In the >age 50 cohort incidence of diabetes treated with insulin from diagnosis is 149/100000, and the recruitment target is 5% of expected incidence at recruiting sites. For non insulin treated participants diagnosed with diabetes after age 50 the recruitment target represents <1% of expected incidence at recruiting sites. A 18 month window for recruitment means we should be able to invite a large proportion of eligible participants through regular screening of practice records or hospital records or writing to participants identified through the retinal screening service (all newly diagnosed patients are referred for retinal screening). A pilot study for this project is currently running at the Exeter site and 27 participants have been recruited by identification through routine care and secondary care records in a period of 4 months at this one recruiting site.

### 9.3 Statistical analysis

Analysis will be pre-registered with clinicaltrials.gov. Both analysis and reporting will conform to STARD and TRIPOD (34, 35). We will assess the discriminative ability of the clinical probability model for early insulin requirement and perform updating if necessary. We will identify discriminatory biomarkers (alone and in combination with clinical features) using logistic regression and generate updated models integrating both clinical features and discriminatory biomarkers (26). Where appropriate covariates will be log transformed, or if necessary recoded into categories. Independent discriminators will be combined using backward stepwise approaches to enter explanatory variables (using predefined candidate co-variates as below), with the combination of variables assessed by the Deviance statistic. Performance of the resulting models will be assessed using Receiver Operating Characteristic (ROC) analysis. Incremental benefit of additional characteristics in nested models will

be assessed using Net Reclassification Improvement and internal validation using bootstrapping and assess goodness of fit. Analysis will be performed separately for participants diagnosed before and after age 50. Model predictions for the >age 50 cohort will be adjusted to reflect population incidence of Type 1 diabetes in this age group using data from Clinical Practice Research Datalink.

Candidate clinical features and biomarkers which will be assessed and where appropriate integrated into prediction models include:

Model development on cross sectional data	Additional features assessed in prospective study only
Age at diagnosis BMI Waist hip ratio Ethnicity Gender Family history diabetes (1 st degree relative) Diagnosis HbA1c, glucose, lipid profile	Symptoms at diagnosis (thirst, polyuria, weight loss (patient reported)) Ketosis (hospital diagnosis DKA, hospital/GP ketone level (urine dip/ capillary) where tested) Acanthosis Personal and family history of autoimmune disease (thyroid, IBD, coeliac, pernicious anaemia, vitiligo, Addison's, rheumatoid arthritis) Hypertension C-peptide & islet autoantibodies (GAD, IA2, ZnT8), Type 1 diabetes genetic risk score (T1DGRS), CRP

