#### Secondary objectives

To prospectively validate a clinical prediction model developed from cross sectional datasets in predicting rapid insulin requirement in young onset diabetes.

To integrate discriminative and additive biomarkers into the clinical prediction model.

To establish a bio resource for future biomarkers discovery and assessment.

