#### 4. STUDY DESIGN

Prospective observational study. We will recruit a prospective cohort of 1200 adults diagnosed with diabetes within the previous 1 year and aged between 18 and 50 at the time of diagnosis.

We will also recruit an additional cohort of 800 participants diagnosed with diabetes in the last year aged >50 at diabetes diagnosis, with recruitment stratified by insulin treatment (400 insulin treated, 400 non insulin treated).

At baseline (visit 1) blood & urine samples will be collected for biomarker assessment and biobanking, and clinical features recorded. We will follow participants for 3 years with annual remote contact (phone, email or letter) and postal urine or capillary blood sample for C-peptide. A further face to face visit with blood & urine sampling will be performed at 3 years.

We will assess the utility of adding biomarkers to clinical features in diagnosing diabetes subtype (defined by insulin requirement at 3 years), and where utility is shown, integrate these into a probability model.

Please also refer to the study summary flow chart on page 7 for a summary of study procedures.

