## 9 STATISTICS AND DATA ANALYSIS

### 9.1 Sample Size

#### *Diagnosis <= age 50 cohort*

Assuming conservative estimates that 25% of participants will have Type 1 diabetes (18) and 80% of participants will have the primary outcome measure a sample size of 1000 (<50 cohort) will give confidence intervals of 85-94% and 87-92% around a biomarker sensitivity/specificity of 90% for Type 1 diabetes (33).

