## 16. SCHEDULE OF AMENDMENTS

Amendment No.	Protocol version no.	Date issued	Author(s) of changes	Details of changes made
SA01	2.0	13jan17	[name]	Extend recruitment to patients diagnosed over the age of 50 who are insulin treated and recruit an additional 400 patients to this older cohort of patients.
SA02	3.0	19 Sept 17	[name]	Extend recruitment of the cohort diagnosed at >50 years to include 400 non-insulin treated patients to be recruited at selected sites.  Remove the word 'young' from the full study title to reflect the inclusion of the older cohort and avoid any misunderstanding of inclusion criteria.  Extend the recruitment period to 30 th September 2018 and increase the number of recruiting sites.

				
Funder details updated to include additional grant from Diabetes UK.
 
Update the AE/SAE reporting procedures in line with Sponsor requirements and agreement.
 
Update the means of contact for follow-up visits to include by post or in person.
 
Promotion of the study on appropriate website and social media.

SA03	4.0	28 Aug 18	[name]	
To extend the recruitment period to 31 December 2019.
 
To modify recruitment criteria for cohort 1 to continue to recruit a further 200 participants receiving insulin treatment diagnosed after age 30 (total cohort 1 participants 1200), and cease recruiting other participants in this cohort.
 
To include the option of capillary blood collection for C-peptide analysis at follow-up in accordance with participant preference.

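### Section 9.3 selects predictors by backward elimination from about 22-43 candidate terms on roughly 190-280 Type 1 cases per cohort, and states no correction of the selected coefficients before the calculator is released

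*Protocol*

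**What the plan says.** Protocol section 9.3 builds the combined logistic models as follows: "Independent discriminators will be combined using backward stepwise approaches to enter explanatory variables (using predefined candidate co-variates as below"), with combinations judged by the deviance statistic. No retention threshold is given. The analysis is run separately for diagnosis before and after age 50. Performance is assessed by ROC analysis, added value in nested models by Net Reclassification Improvement, and internal validity by bootstrapping together with goodness of fit. Over-50 predictions are then adjusted to population incidence.

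The same section says that an existing clinical model will be assessed and, if necessary, updated. One secondary objective in section 3 reads: "To integrate discriminative and additive biomarkers into the clinical prediction model". Section 14 sends the result to clinicians and patients as a website calculator and an app.

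Section 9.1 sizes the 50-and-under cohort for the precision of one biomarker's sensitivity and specificity: "Assuming conservative estimates that 25% of participants will have Type 1 diabetes (18) and 80% of participants will have the primary outcome measure", with "a sample size of 1000 (<50 cohort"). Section 4 now sets a larger target: "We will recruit a prospective cohort of 1200 adults diagnosed with diabetes within the previous 1 year". The amendment schedule describes the addition as a "further 200 participants receiving insulin treatment diagnosed after age 30 (total cohort 1 participants 1200").

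**The concern.** Backward elimination keeps a term partly because its estimate happened to be large in this sample. The retained coefficients are therefore biased away from zero, and some null terms survive. The resulting model is too extreme in new patients: high probabilities are too high, low ones too low, and the apparent AUC is optimistic.

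Bootstrapping as internal validation measures this optimism but does not remove it from the published equation. If only the final model is resampled, most of the selection effect is not measured either. Section 9.3 does not say that selection is repeated in each resample, or that the coefficients are corrected before release.

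This matters because the product is an individual probability shown to clinicians and patients, and because the primary objective asks what biomarkers contribute alone and in combination with clinical features. The over-50 incidence adjustment does not by itself correct a slope.

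**Working it through.** **1. The plan's own figures.** Cases = N x outcome availability x prevalence.
- 50 and under (section 9.1): 1000 x 0.80 x 0.25 = 200 cases and 600 non-cases. Exact 95% intervals around 90% are 85.0-93.8% and 87.3-92.3%, which match the stated 85-94% and 87-92%.
- Over 50 (section 9.1): 800 x 0.90 x 0.26 = 187 cases and 533 non-cases. Exact intervals are 84.8-93.9% and 87.1-92.4%, which also match.

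**2. Current 50-and-under target.** 1200 x 0.80 x 0.25 = 240 cases. If the added 200 insulin-treated participants have 48% prevalence (section 9.1's figure for insulin-treated participants over 50, assumed here to carry over), the count is 200 + 200 x 0.80 x 0.48 = 277.

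**3. Candidate terms (table in 9.3).**
- Each group as one term: 9 in the cross-sectional column and 13-14 in the prospective column, so 22-23.
- Ethnicity and lipids as 3 terms each, ketosis as 2, and autoimmune history as 2: 13 + 15 = 28.
- Seven autoimmune diseases entered separately for patient and family: 28 - 2 + 14 = 40. Finer coding takes this to about 43.

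**4. Cases per candidate term.**

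| Cohort and cases | 22 terms | 28 | 40 | 43 |
|---|---|---|---|---|
| >50, 187 | 8.5 | 6.7 | 4.7 | 4.4 |
| <=50, 200 | 9.1 | 7.1 | 5.0 | 4.7 |
| <=50, 240 | 10.9 | 8.6 | 6.0 | 5.6 |
| <=50, 277 | 12.6 | 9.9 | 6.9 | 6.4 |

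**5. Expected shrinkage of the unselected model.** Solve S = 1 + p / (n ln(1 - R2/S)), where R2 is the Cox-Snell value. With an assumed Nagelkerke R2 of 0.5 and n = 720 at 26% (Cox-Snell 0.341), S = 0.92 for 28 terms and 0.89 for 40. With n = 960 at 25% (0.338), S = 0.94 and 0.91. At an assumed Nagelkerke R2 of 0.3, S is 0.86 and 0.81 for n = 720, and 0.89 and 0.85 for n = 960.

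**6. Simulation of backward elimination without shrinkage.** The main setting used 28 or 40 independent candidates (5 strong, 5 weak at log-odds 0.2 per SD, the rest null), true AUC about 0.80 or 0.90, 300 runs per scenario, and slopes measured in 40,000 new subjects.
- n = 800 or 720: mean slope 0.85-0.91 at p<0.05 and 0.80-0.88 at p<0.157. Retained weak terms were inflated 1.36-1.66 and 1.22-1.50 fold.
- n = 960 with 240 or about 277 cases, 22-40 terms, 5% threshold, 100 runs each: slope 0.86-0.90 at AUC 0.76 and 0.90-0.94 at AUC 0.86-0.87. Weak-term inflation was 1.22-1.37 fold. The over-50 cohort in the same setting gave slope 0.79-0.91 and inflation 1.34-1.48.
- A further setting (720 at 26% or 960 at 27%, 22-34 terms, 5% threshold): slope 0.84-0.95 without shrinkage. With selection repeated in each resample, shrinkage and a re-estimated intercept, the slope was 0.96-1.05, with slightly lower probability error in every scenario.

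**7. From slope to probability.** A prediction of 94% has logit 2.75. If predicted and true risk agree at 50%, the true logit is slope x 2.75. A slope of 0.95 gives 93.2% and a slope of 0.80 gives 90.0%, so the overstatement is 0.8-4.0 points. If they agree at the 26% prevalence instead, the true values are 92.8% and 88.0%, an overstatement of 1.2-6.0 points. About 1-5 points is a fair summary.

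**The case against.** The strongest reply is that much of this is detail for a statistical analysis plan that is not at hand. Section 9.3 commits to bootstrapping, goodness of fit, pre-registration and TRIPOD. It nowhere says that raw selected coefficients enter the calculator. A reader might infer that the plan rejects shrinkage, but the document is only silent on it. What remains is that the protocol does fix the selection method and the candidate list, and gives the bootstrap only a validating role.

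Second, the clinical part comes from an existing model that is to be updated. If only the prospective column is added (about 14 terms), there are 187/14 = 13.4 to 200/14 = 14.3 cases per term. That reading is possible. However, the stepwise sentence points to the whole table, and the secondary objective on validating the existing model is limited to young-onset diabetes.

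Third, the 50-and-under count should reflect 1200 recruits. That is correct. It lessens the effect there but does not remove it, and the over-50 cohort gains nothing.

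Two further inferences are tempting. One is that the clinical-only and combined models will not be nested. That would follow only if each were selected separately on the same data, and section 9.3 says nested. The other is that stepwise selection departs from the objective of integrating biomarkers into the clinical model. Section 9.3 speaks of updated models combining both, which fits the objective.

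The inflation also concerns weak terms only. Section 2 gives the genetic risk score an AUC of 0.88, so exaggeration of the main biomarkers is not shown.

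**Conclusion.** The point holds in moderate form. Followed as written, section 9.3 would yield coefficients that are too large in both cohorts. The expected calibration slope is roughly 0.80-0.95, predictions above 90% are about 1-5 points too high, and surviving weak predictors are inflated about 1.2-1.7 fold. The slope is generally nearest to 1 where discrimination is high and in the larger 50-and-under cohort, and the over-50 cohort is the more exposed.

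The case counts follow from the protocol, apart from the 48% assumption behind 277. The term count depends on coding. Effect sizes, independence of predictors, complete predictor data and the retention threshold are all assumed. The protocol does not support the claim that shrinkage is excluded, or that the principal biomarkers will be overstated.

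**What to change.** Add to section 9.3:
1. The entire selection procedure is repeated in every bootstrap resample, in each age cohort.
2. The selected coefficients are multiplied by the resulting optimism-corrected calibration slope and the intercept is re-estimated before the model is released. In the over-50 cohort this precedes the population-incidence adjustment.
3. Optimism-corrected AUC is reported.

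No new data are needed. The costs are wording, computing time, a slightly lower reported AUC and possible slight over-shrinkage (slopes up to 1.05 in the check above).

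For the 50-and-under cohort, an alternative is to enter the existing clinical model's linear predictor as a single term and force in the named biomarkers. That is an option, not a required correction, because its benefit depends on the size and comparability of the source cohorts, which the protocol does not give.

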## STUDY SUMMARY

StudyTitle	STARTRIGHT: Getting the right classification and treatment from diagnosis in adults with diabetes
Internal ref. no. (or short title)	CRF243 (StartRight Study)
Study Design	Prospective observational
Study Participants	Adults who have been diagnosed with diabetes (excluding gestational or secondary diabetes) for $\leq 1$ year at the time of study recruitment. Aged $\geq 18$ at the time of diabetes diagnosis.
Planned Sample Size	Main cohort: 1000 Additional late onset diabetes cohort: 800
Follow up duration	3 years
Planned Study Period	6 years
Study Summary	This study aims to achieve more accurate early classification of diabetes and identification of which patients will rapidly require insulin treatment. We will recruit 1200 participants who have been diagnosed with diabetes in the last year and were aged between 18 and 50 years at the time of diagnosis. We will recruit an additional cohort of 800 participants diagnosed after age 50. We will record clinical features and biomarkers that may help us to determine diabetes type at diagnosis and follow participants for 3 years to assess the development of severe insulin deficiency (measured using C-peptide) and insulin requirement. We will assess utility of clinical features and additional biomarkers in identifying patients with rapid progression to insulin requirement. Findings will be integrated into a freely available clinical prediction model.

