## STUDY PROTOCOL

**StartRight: Getting the right classification and treatment from diagnosis in adults with diabetes.**

### 1 Lay summary

The treatment of Type 1 and Type 2 diabetes is very different. People with Type 1 diabetes rapidly stop making their own insulin, so need insulin injections from diagnosis. People with Type 2 diabetes can keep making their own insulin but it may not work as well as it should, so they can be treated with diet or tablets. While they may eventually need insulin treatment it is usually not until many years after diagnosis.

It is often difficult for doctors to tell which kind of diabetes a person has. Because of this, sometimes people are given the wrong diagnosis. This can have a huge impact as it means they could receive the wrong treatment. A person incorrectly diagnosed with Type 1 diabetes will be prescribed unnecessary insulin injections and miss out on other helpful therapies. A person incorrectly diagnosed with Type 2 diabetes may develop severely high glucose and become unwell with a condition called Diabetic Ketoacidosis if they do not receive insulin treatment.

This study aims to improve this situation by helping doctors more accurately tell the type of diabetes a person has when they are first diagnosed. We will recruit 1000 participants who have recently been diagnosed with diabetes between the ages of 18 and 50. We will recruit an additional 800 recently diagnosed participants who developed diabetes after age 50, half of whom will be receiving insulin therapy. We will record clinical features and measure blood tests that may help us determine diabetes type at diagnosis and follow participants for 3 years to see whether they stop producing their own insulin and need insulin treatment, which confirms Type 1 diabetes. We will assess whether clinical features and blood tests can help us tell if a patient needs rapid insulin treatment and should be initially treated as Type 1 or Type 2 diabetes.

We will combine results from this study and existing previous studies to produce a calculator, called a clinical probability model that will allow doctors and patients to combine information from clinical features and (where necessary) blood tests to accurately diagnose what type of diabetes a person has and therefore give the correct treatment. This will be freely available to doctors and patients as a website calculator and smartphone app.

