#### **5.1.2 Targeted recruitment of participants aged over 50 by insulin treatment status**

To ensure sufficient prevalence of the primary study outcome of Type 1 diabetes in those over age 50 recruitment of this age group will target equal numbers (400 each) of participants receiving insulin treatment at the time of recruitment (high prevalence Type 1), and those not receiving insulin treatment (low prevalence Type 1). This will be managed using separate recruitment targets for these subgroups, based on prior recruitment rate, with recruitment to the non insulin treated cohort limited to a subset of study sites.

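### Section 9.3 ties only the over-50 models to the population, although 200 of the 1200 younger participants are also selected on insulin treatment

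*Protocol*

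**What the plan says.** Protocol section 9.3 analyses participants diagnosed before and after age 50 separately. For the older group it states that "Model predictions for the >age 50 cohort will be adjusted to reflect population incidence of Type 1 diabetes in this age group", with the Clinical Practice Research Datalink as the source. It gives no counterpart for the younger group.

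The current target for the younger group is 1200. Section 4 has "We will recruit a prospective cohort of 1200 adults diagnosed with diabetes within the previous 1 year and aged between 18 and 50", and the Study Summary text has "We will recruit 1200 participants who have been diagnosed with diabetes in the last year and were aged between 18 and 50 years". The schedule of amendments (section 16, SA03) explains who the last 200 are. Its wording is: "continue to recruit a further 200 participants receiving insulin treatment diagnosed after age 30 (total cohort 1 participants 1200), and cease recruiting other participants". The cohort meant is the younger one. SA03 is used here only to explain the current figure of 1200.

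Section 5.1.2, on the over-50 cohort, shows how the protocol itself reads selection on insulin: it sets targets for "participants receiving insulin treatment at the time of recruitment (high prevalence Type 1), and those not receiving insulin treatment (low prevalence Type 1").

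Other current text still gives 1000 for the younger cohort:
- The Planned Sample Size row of the Study Summary has "Main cohort: 1000".
- The Lay summary has "We will recruit 1000 participants who have recently been diagnosed with diabetes between the ages of 18 and 50".
- Section 9.1 has "a sample size of 1000 (<50 cohort) will give confidence intervals of 85-94% and 87-92" per cent.

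**The concern.** Both cohorts are now recruited partly on insulin status, but only one has a planned correction. Selection is on insulin at recruitment. The primary outcome is insulin treatment plus low C-peptide at 3 years (section 3). The two differ but are closely linked: section 9.1 gives Type 1 prevalences of 48% and 3.9% in insulin-treated and untreated people over 50. Insulin at recruitment is not in the candidate list of section 9.3. The listed candidates may explain part of the selection, but the plan cannot rely on them to explain all of it.

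The planned internal checks would not show the shift. Bootstrapping and goodness of fit use the same enriched sample, and a logistic model with an intercept reproduces the event rate of the sample it was fitted on. In the prospective validation (a secondary objective), a model well calibrated to unselected participants would appear to under-predict at ages 31–50. The updating that section 9.3 allows could then move it upwards. The product is a public calculator (section 14), so the predicted probability itself is what users receive.

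**Working it through.** **1. The plan's own figures.** Section 9.1, younger cohort: 1000 × 0.80 = 800 with outcome; 25% gives 200 Type 1 and 600 Type 2. Exact 95% intervals are 85.0–93.8% for 180/200 and 87.3–92.3% for 540/600, which match the stated 85–94% and 87–92%. Section 9.1 is therefore calculated for 1000 without the added 200.

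**2. Crude prevalence with the 200 added.** Prevalence = (1000p + 200q)/1200, where p is the Type 1 share in the first 1000 and q the share in the added 200. The protocol does not give q for this group. Two borrowed values bracket it: 48% (section 9.1, over-50 insulin treated) and 74% (the complement of the 26% misclassified among people given insulin from diagnosis, section 2). p = 25% is the planning value; 35% is an assumption.

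| p | q | Prevalence | Odds relative to p |
|---|---|---|---|
| 25% | 48% | 346/1200 = 28.8% | 1.22 |
| 25% | 74% | 398/1200 = 33.2% | 1.49 |
| 35% | 48% | 446/1200 = 37.2% | 1.10 |
| 35% | 74% | 498/1200 = 41.5% | 1.32 |

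At p = 25%, the added 200 supply 96/346 = 27.7% to 148/398 = 37.2% of all Type 1 cases.

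**3. Shift given covariates x, ages 31–50.** Treat the added 200 as random draws from the same insulin-treated group, and let k = 200/N, where N is the number insulin treated and diagnosed after 30 among the first 1000. The odds of Type 1 are multiplied by

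[1 + k·P(ins|T1,x)] / [1 + k·P(ins|T2,x)].

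None of these inputs is in the protocol. Assume P(ins|T1,x) = 0.9 and N = 150, 250 or 400:

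| N | k | P(ins\|T2,x) = 0.1 | 0.5 | 0.9 |
|---|---|---|---|---|
| 150 | 1.333 | 1.94 | 1.32 | 1.00 |
| 250 | 0.8 | 1.72/1.08 = 1.59 | 1.72/1.40 = 1.23 | 1.00 |
| 400 | 0.5 | 1.38 | 1.16 | 1.00 |

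At k = 0.8, a 30% probability (odds 0.4286) becomes 40.6%, 34.5% or 30.0%. The factor is 1 when insulin use no longer depends on type once x is known.

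**4. Precision of the enriched 1200, unweighted, 80% followed up.**
- q = 48%: 249/277 gives 85.7–93.2% and 615/683 gives 87.5–92.2%.
- q = 74%: 286/318 gives 86.1–93.0% and 578/642 gives 87.4–92.2%.

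Precision is not harmed by the enrichment.

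**5. Cost of weighting back to the mix before the restriction.** Give the insulin-treated, diagnosed-after-30 stratum weight w = N/(N + 200) and everyone else weight 1. The Kish effective size is 1000² / [(1000 − N) + (N + 200)w²]:
- N = 150, w = 0.429: 1094
- N = 250, w = 0.556: 1125
- N = 400, w = 0.667: 1154

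**The case against.** The strongest reply is that this is an omission, and the statistical analysis plan is not at hand. Section 9.3 neither rules out weighting in the younger cohort nor says that all 1200 will be used unweighted. That would carry more force had the protocol left population adjustment open. Instead it fixes the adjustment and confines it to one of two cohorts selected on insulin.

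The cohorts do differ in degree. The over-50 cohort is set at 400/400 by design, and section 9.2 puts recruitment at 5% of expected incidence in the insulin treated against under 1% in the others. The younger cohort's enrichment is 200/1200 = 17%. That makes the need smaller, but does not remove it.

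The following points stand and limit the claim:
- The conditional shift may be nil. Candidates such as ketosis, diagnosis HbA1c, C-peptide, autoantibodies and the genetic risk score plausibly account for much early insulin use.
- Neither 48% nor 74% describes insulin-treated people diagnosed between 30 and 50.
- The first 1000 need not represent the population, since sites recruit through different routes (section 5.1.1). Over-prediction relative to the population is therefore not established.
- Combining with earlier studies (section 1) may dilute the shift.
- Sensitivity and specificity, the core of the primary objective, do not depend directly on prevalence.
- The mismatch between 1000 and 1200 is a separate, editorial matter.

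**Conclusion.** The concern holds and should be fixed, with medium confidence. Followed as written, section 9.3 can be expected to raise predicted Type 1 probabilities at ages 31–50 relative to participants not selected on insulin, and nothing it plans would correct this. The direction rests on two things: the link between insulin and outcome that the protocol itself states, and the absence of insulin from the candidate predictors. The size rests on assumptions and runs from no shift to nearly a doubling of the odds. The effect falls on calibration and prevalence-dependent measures, which belong to the secondary objectives and the calculator. The conflict between 1000 and 1200 is certain and needs no assumption.

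**What to change.** In section 9.3, extend the adjustment to the younger cohort: weight or recalibrate by stratum (insulin treated and diagnosed after 30, versus the rest), preferably to the population source already named for the over-50 cohort. As a sensitivity analysis, report calibration and prevalence-dependent measures in participants recruited before the restriction, noting that they were not selected on insulin but need not be population-representative.

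Separately, reconcile 1000 and 1200 across the Study Summary, Lay summary, section 4 and section 9.1, and restate the case numbers and intervals in 9.1 for 1000 plus 200 enriched.

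The cost is wording. Treatment details are already collected at baseline, and age at diagnosis is both an eligibility criterion and a candidate predictor. Weighting back to the mix before the restriction widens intervals slightly compared with an unweighted 1200, but the effective size stays above 1000. The cost of weighting to population shares cannot be computed from the protocol.
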